2. Orientation to the technology (in person meeting): A member of the research team will meet with each participant to orient them to both the wireless health and fitness tracking sensor, other health applications and the mHealth dashboard in UC Davis' Electronic Health Record, EPIC. The selected sensors and applications will track numbers of steps traveled, approximate calorie expenditure based on movement, sleep quality, heart rate, and components of logged nutrition data. The data wirelessly uploads to the participant's personal, or study supplied, Apple device (iPhone, iPad, or iPod), allowing the participant to develop awareness of typical activity and to work toward goals to improve activity levels. The mHealth platform/dashboard will allow the health coach and participant a secure space to share the data generated by the participant through the sensor, to view activity trends, and to create and track progress toward specific, measurable, attainable, relevant and time bound goals. Data elements shared to the electronic health record include: steps traveled, activities performed in minutes, calorie expenditure, and logged nutrition data. Participants can access EPIC MyChart (web page/portal) through a smartphone, tablet, or personal computer. The research team will provide individual training on the use of the technology.

3. Five bi-weekly support calls (15-30 minutes each; over 3 month intervention period): Calls will be scheduled at times chosen by the participant. The purpose of these calls is to review progress and discuss approaches to solving problems in reaching goals. On each call, the coach and participant will review the patient-generated activity data from the sensors and compare in relation to goals. They will observe and discuss trends in the data that may provide opportunities for reinforcement and highlight opportunities for continued behavior change. Following each session, the nurse coach will enter details about the current goal set by the patient, a snapshot of progress made toward goals and other relevant information into the mHealth Dashboard so that the patient, the provider and the nurse can all track and review progress.

Patient and Provider Engagement and Empowerment through Technology $(P^2E^2T^2)$ to Improve Health in Diabetes

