Historical data, such as completed lab work values as identified above (Study Endpoints section), will be gathered by querying the EHR for all participants involved in the study. This will be accomplished by working with the Health Informatics for research group, led by [name].

All data and data identifiers related to this study will be destroyed seven years after completion of the study. All data findings from the study will be presented as aggregate data with no individual subject identifiers.

Subjects will be using commercial off-the-shelf (COTS) sensors, smart phone applications, and web-based physical activity dashboard technologies. Participants must agree to use the sensors and applications required for data collection. If they are unwilling to use this sensor, they will not be able to participate. Immediately following consent and randomization into the "Care Coordination" and "P²E²T²" arms, project staff will assist participants with technology set-up, configuration, use, and ensure that subjects understand the commercial terms of service agreements, before they begin the trial. In order to further protect individual privacy, subjects in the P²E²T² arm may choose to share with their coach only portions of the data streams from their devices/apps. That is, subjects have the option to filter the data streams shared with their coach by time of day, and specific metric (i.e. steps counted, calories burned, etc.).

Variable	Measure	Data Collection		
v ar lable	Measure	Baseline	3 months	9 Months
Age, Gender,	Demographic Data Form	Х		
Race/Ethnicity, Education				
Level, Income Level and				
Insurance Type				
Specific Aim 1				
Focus Groups		Х	Х	Х
Specific Aim 2				
Self-Efficacy	Diabetes Empowerment Scale –	Х	X	Х
	Short Form (DES-SF)			
Readiness to Change	Readiness to Change Survey	Х	Х	Х
Clinical Indicators	Electronic health record	Х	Х	Х
(Abstracted)				
	Patient Health Questionnaire	Х	Х	Х
	depression scale-9 (PHQ-9)			
Quality of Life	Perceived Stress Scale (PSS)	Х	X	Х
Quality of Life	PROMIS Measures – Physical	Х	X	Х
	Function SF, Emotional Distress			
	SF, Sleep Disturbance			

15) Provisions to Monitor the Data to Ensure the Safety of Subjects

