All subject questionnaires will be reviewed by the nurse researcher for the presence of mood symptoms that may require further assessment and possible intervention. If a participant relates information to any of the study personnel that leads the study personnel to believe the participant is a risk to themselves or others, immediate consultation with the principal investigator (HY) will be obtained. The lead nurse investigator for this study, [name], is qualified to monitor and quickly address high-risk behaviors observed and reported by the nurse coaches. Should a safety issue become apparent in the course of interacting with the participant, appropriate referrals will be made, the event will be documented, and if necessary the IRB will be notified. Appropriate referrals may be to crisis hotlines, the participant's health care provider, or law enforcement as needed and deemed appropriate by the PI. There is a minimal risk that a subject's safety could be compromised by sharing historical data about activity. This risk is minimized with regard to this study, because only the intervening coach will have personal identifying information that links the participant with their coded activity data due to the personal and interactive nature of the coaching process. Activity data that is analyzed and health coaching worksheets filled out by the coach will be coded and no personal identifiers will be available to the rest of the research team at the point of analysis. Due to the commercial availability of these apps, investigators cannot prevent study subjects from sharing their data with other individuals should an individual choose to share their data.

Patient and Provider Engagement and Empowerment through Technology $(P^2E^2T^2)$ to Improve Health in Diabetes

16) Withdrawal of Subjects

Subjects may withdraw from the study at any time without harm or prejudice. If the participant would like their data to be removed from the study, any data or paperwork related to the participant will be immediately destroyed. If they consent to allowing data already collected to be kept, this data may remain in the study.

17) Risks to Subjects

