There are little to no health risks associated with participation in this study and it is expected that participants receiving activity tracking and/or health coaching may receive some benefit. Increasing physical activity in incremental stages has known health benefits and low risk. The study does not involve diagnosis or treatment and targets health improvement rather than disease of a sensitive nature. There is possibility of loss of confidentiality, but appropriate steps will be taken to minimize those risks including coding of questionnaire and nurse coaching worksheets and maintenance of all data on secure, password protected servers. Additionally, subjects selected into one of the two treatment arms will be specifically counseled about potential losses of confidentiality relative to their use of commercial off-the-shelf (COTS) technology for health monitoring. What is learned may help improve diabetes care and diabetes management in general. For persons with sensitive skin, there is a slight risk that some of the assigned technology may cause skin sensitivity. If this occurs, the participants will be advised to stop using the technology immediately, and contact the study team. Alternative technology will be provided to mitigate the problem if the subject choses to continue participating in the study.

18) Potential Benefits to Subjects

Subjects receiving feedback about their health behaviors through technology or technology plus health coaching may benefit from increased awareness of their daily habits. Subjects receiving health coaching may benefit from receiving individual counseling and support for healthy behavior change that encourages the adoption of healthy behaviors including dietary changes and physical activity. Subjects receiving no intervention are not expected to benefit from this study. Subjects receiving the tech-plushealth-coaching interventions may or may not benefit from their participation.

19) Vulnerable Populations

No vulnerable populations will be included in this study

20) Multi-Site Research n/a

21) Community-Based Participatory Research n/a

Patient and Provider Engagement and Empowerment through Technology $(P^2E^2T^2)$ to Improve Health in Diabetes

22) Sharing of Results with Subjects

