Patient and Provider Engagement and Empowerment Through Technology Program to Improve Health in Diabetes

PI: [name]

January 11, 2019

NCT number: NCT02672176

Analytical and Statistical approaches

We will use Stata v15.0 (Stata Corp, College Stations Tx 2017) for all statistical analyses. Descriptive analysis will yield means/standard deviations for continuous variables and frequencies for categorical variables. We will examine distributions to determine whether data meets assumptions for planned statistical analyses. We will compare patient demographic and health-related characteristics between the individuals in the intervention group and the usual care group. We will compare continuous variables using a Student's t test or the Wilcoxon Signed-Rank test, and will compare categorical variables using the chi-squared test and Fisher's exact test, as appropriate. We will compare number of steps per week at baseline (Week 2) versus 3 months (Week 13), baseline versus 9 months (Week 37) and 3 months versus 9 months, using a paired t-test to evaluate the change in physical activity over time.

We will calculate change in outcomes over time as the difference between baseline and 3 months, and baseline and 9 months for diabetes self-efficacy scores, depression severity (PHQ-9), patient stress score, and PROMIS measures (Emotional distress anxiety, and physical functioning). We will use Student's t test to compare the change in outcome between usual care and intervention groups (Significance level: $p \le .05$).

In the primary analysis, we will estimate the difference over time in the effects of the intervention over usual care in the study participants. This is an intent to treat analysis, with the assumption that any dropouts are missing at random. We will also use an analytical method (Mixed model) which accounts for the missing data contributed by participants who dropped out from the study. Lastly, we will conduct a sensitivity analysis to determine whether there is a difference with regards to the significance of our findings when we exclude participants who drop out from the analysis. All participants, regardless of intervention completion, will be included in the intent to treat analysis.

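### The SAP compares weekly step counts with no wear or valid-day rule, so a difference in sensor wear between weeks can appear as a change in physical activity

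*SAP*

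**What the plan says.** The step analysis is one sentence in the SAP, Analytical and Statistical approaches. It begins "We will compare number of steps per week at baseline (Week 2) versus 3 months (Week 13", goes on to baseline against 9 months (Week 37) and 3 against 9 months, and ends "using a paired t-test to evaluate the change in physical activity over time". The variable is a count over a single week, and the paired difference is read as change in activity.

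The SAP's missing-data text is about participants who drop out. Its mixed models name self-efficacy, depressive symptoms and perceived stress, not steps. Neither part covers a participant who stays in the study but wears the sensor on some days only.

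Four places in the protocol bear on what a weekly count contains:

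- Section 12 (Procedures Involved): "Data elements shared to the electronic health record include: steps traveled, activities performed in minutes, calorie expenditure, and logged nutrition data".
- Section 14 (Data Management and Confidentiality), for the intervention arm: "subjects have the option to filter the data streams shared with their coach by time of day, and specific metric", with the examples "i.e. steps counted, calories burned, etc".
- Section 15 (monitoring for safety): "Activity data that is analyzed and health coaching worksheets filled out by the coach will be coded". It does not say whether these data are filtered or unfiltered.
- Section 17 (Risks to Subjects), for skin sensitivity: "the participants will be advised to stop using the technology immediately, and contact the study team". It adds: "Alternative technology will be provided to mitigate the problem if the subject choses to continue participating in the study".

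**The concern.** A weekly count is the product of how active a person is and how much of the week is recorded. The SAP attributes the whole difference between two weeks to the first factor, and neither document has a rule that separates it from the second. No minimum number of days is set, no averaging over worn days is specified, and nothing says whether a day without data is zero or missing.

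The protocol itself foresees gaps and changes of instrument (Section 17). The conditions of use also differ between the compared weeks: coaching with review of sensor data runs over the first 3 months, and Week 37 lies about six months after it ends.

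At stake is the only sensor-measured activity result in the SAP. The protocol's Background presents sensor data as the answer to reliance on self-reported activity in the earlier coaching study. A gain or decline produced by wear would defeat that purpose.

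**Working it through.** **Plan's own figure.** Neither document gives a sample size, SD, expected change or wear level for steps, so there is none to reproduce.

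**Step 1: exact arithmetic.** Write the weekly count as T = D × S × (1 − f), where D is days worn, S is true steps per worn day, and f is the share of steps hidden by a filter (f = 0 if the unfiltered stream is analysed). With S unchanged and f = 0, the relative change is D(later) / D(earlier) − 1:

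- 7 to 6 days: 6/7 − 1 = −14.3%
- 7 to 5 days: 5/7 − 1 = −28.6%
- 7 to 4 days: 4/7 − 1 = −42.9%
- 6 to 7 days: 7/6 − 1 = +16.7%

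These percentages do not depend on the daily step level. The error can run either way.

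**Step 2: filtering, only if the filtered stream is analysed.** With D and S unchanged, the change is (1 − f(later)) / (1 − f(earlier)) − 1. Newly hiding hours that hold 25% of steps gives −25%. The same filter in both weeks gives 0.

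**Step 3: effect on the planned test.** A simulation applied the paired t-test with zero true change, 1,500 runs per cell. The inputs are assumptions, because the documents give none: mean 5,000 steps a day, between-person SD 2,000, day-to-day SD 1,500, and mean wear of 6.5 days in Week 2. Worn days are drawn independently in each week and are unrelated to activity. The test is two-sided at 0.05; the SAP states this for its model effects and gives no level for the step test. The comparison variable is mean steps per worn day among those with at least 4 worn days in both weeks. Of the pair numbers, 150 and 100 are the protocol's planned and reduced numbers per arm, and 50 is an added lower case.

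| Later mean wear (days) | Mean change in weekly count | Weekly count: rejections at n = 50 / 100 / 150 | Steps per worn day: rejections at n = 50 / 100 / 150 |
|---|---|---|---|
| 6.5 | about 0 | 4.8% / 4.3% / 5.1% | 5.3% / 4.1% / 4.7% |
| 6.0 | about −2,500 | 58% / 86% / 96% | 4.5% / 5.6% / 5.1% |
| 5.5 | about −5,000 | 98% / 100% / 100% | 4.7% / 4.5% / 5.1% |
| 5.0 | about −7,500 | 100% / 100% / 100% | 4.7% / 5.1% / 4.9% |

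The mean changes agree with direct arithmetic: 5,000 × 0.5 = 2,500, 5,000 × 1.0 = 5,000 and 5,000 × 1.5 = 7,500. Under these inputs, an average loss of half a worn day is enough to make a null result look real in most runs at n = 100. With equal wear, the weekly count behaves correctly.

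**The case against.** The best reply is that the SAP is silent rather than wrong: it does not say that the count is an unprocessed sum or that unworn days are zero, and an analyst might apply a sensible wear rule. That is fair as to intent. But the named variable is a weekly count, and followed as written it mixes wear with activity. Section 14 makes agreement to use the sensors a condition of taking part, which is not a rule about days worn.

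A reader might infer three stronger things that the documents do not support:

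- **That filtered steps enter the analysis.** Section 14 describes the filter only for data shared with the coach. Sections 6, 12 and 26 place activity data in the same record system that the coach uses, so it is possible, but no section names the source of the analysed steps. Even then, an unchanged filter creates no false change. A participant who withholds steps altogether has a missing week and leaves the pair, which is a selection problem, unless the week is stored as zero.
- **That the direction is known**, with wear high during coaching and low afterwards. This is plausible, but neither document reports wear. Wear could equally be highest in Week 2, when the device is new, and the Week 2 to Week 13 error would then run against the intervention.
- **That the trial's main results are at risk.** Steps are not among the endpoints in Section 11 or the measures in the Section 14 table. Under Section 9, Care Coordination participants receive the device only after completing all questionnaires. The step test is an uncontrolled within-person comparison.

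The device change is a small matter: Section 17 rates skin sensitivity as a slight risk and gives no frequency.

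**Conclusion.** The point holds for wear. As specified, the step comparison cannot tell a change in days worn from a change in activity. The shift is proportional to wear: −14%, −29% or −43% for 7 days falling to 6, 5 or 4, and +17% for 6 rising to 7. These figures assume only constant steps per worn day. The rejection rates rest on assumed step levels, SDs and wear, and show sensitivity, not what happened in this trial, where direction and size are unknown.

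For filtering the point is conditional: it applies only if the filtered stream is analysed and the filter changes between the compared weeks. The consequence is confined to a secondary within-person analysis, and the randomised comparisons are untouched. The correction is still worth making, because a standard replacement variable removes the dependence on the number of days worn.

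**What to change.** In the SAP, replace the weekly count with mean steps per valid day in each of Weeks 2, 13 and 37, and add:

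1. A valid-day rule and a minimum number of valid days per week, set before analysis from what the day-level data can support. Any threshold, such as 4 days, is an example. A step floor should be checked so that it does not remove truly inactive days.
2. Unworn or filtered days are missing, not zero. This matters for time-of-day filters, because a partly hidden day would also lower a per-day mean.
3. Valid days per week are reported beside the step result.
4. A statement of whether the filtered or unfiltered stream is analysed.
5. A flag on pairs that span a device change.

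The cost is SAP wording, some data handling, and the loss of participant-weeks with too few valid days. Two limits should be acknowledged. The SAP is dated January 2019 and the protocol planned completion by the end of 2017, so the rule may have to rest on data already held. The elements listed in Section 12 as going to the health record do not include wear time, and no section says that filter settings are logged. Also, a per-valid-day mean assumes that worn days represent unworn ones; reporting valid days lets a reader judge this but does not prove it.

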9) Compensation to the Subjects

All subjects, regardless of treatment arm, will be given a health monitoring device at the end of the study. Upon completion of study questionnaire and their regularly scheduled visit with their primary care physician all participants will receive \$50 at baseline, 3 and 9 months. Those participants in the intervention $(P^2E^2T^2)$ arm will receive a health monitoring device at the beginning of the study; and those participants in the Care Coordination arm of the study will also receive a health monitoring device upon successful completion of all study questionnaires. If participants do not complete all aspects of the study, they will not receive the health monitoring sensor device. Each sensor device is worth approximately \$75.

10) Study Timelines

Each individual will be enrolled in the study for 9 months. Each participant will complete a study questionnaire at baseline, 3 months and 9 months. Estimated duration of the study completion is 24 months from start of enrollment (January 1^{st} , 2016 – December 31^{st} , 2017).

11) Study Endpoints

Outcomes to be evaluated include: i) Quality of Life (QOL) measures; ii) Self-efficacy; iii) Readiness to Change; and iv) Clinically Relevant Indicators (HgbA1C, HDL, LDL, triglycerides). All measures will be collected in both groups at the study timelines. At baseline (time of recruitment), all participants will be asked to complete the surveys and the care coordinator will request the primary care provider orders for the laboratory tests measuring the clinical indicators. The lab tests are routinely used to monitor diabetes management and are typically covered by insurance. Should the patient not have a payment source for the laboratory assays, the project will cover the cost of the laboratory tests. At 3 months and 9 months, surveys links will be sent by email to each participant along with a reminder to complete the laboratory work ordered by their provider. If not completed, reminder emails or phone calls may be made by the study team. The primary endpoints of the study are: baseline data; data at the completion of five sessions of support calls during the 3 months of the intervention; and data at 6 months after the end of the intervention (9 months after baseline).

12) **Procedures Involved**

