We will use multivariate regression modeling for all hypotheses testing to estimate withingroups and across group effects of the intervention on the outcome (significance level: $p \le$ 0.05). The mixed effects models will evaluate the impact of the intervention over time in the outcomes of Diabetes Self-Efficacy, depressive symptoms, and Perceived Stress Score (PSS). We will include a binary indicator for intervention group assignment, and a group- by-time interaction term in the models to compare improvement over time between the intervention group and usual care group. We will assess all variables for collinearity before including in the model. We will evaluate model fit using deviance tests for nested models, the Akaike Information Criterion, and the Bayesian Information Criterion for non-nested models. We will assess the estimates for the fixed effects using a pre-determined significance level (p < 0.05) on two sided tests and 95% confidence intervals. We will use the same approach for analyzing primary and secondary outcomes analyzing the effect of the intervention at baseline, 3 and 9 months.

We will conduct a post-hoc analysis examining the relationship between stage of change at baseline and intervention outcomes. We hypothesize that there might be differences in who the intervention benefits most – and will explores whether readiness to change status might be a tool for screening potential participants for inclusion in future trials or interventions.

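### Steps are compared at three single weeks by separate paired t-tests, so each contrast keeps only complete pairs, the three need not add up, and step data from other weeks go unused

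*SAP*

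**What the plan says.** The first paragraph of the SAP (Analytical and Statistical approaches) covers steps in one sentence. It begins "We will compare number of steps per week at baseline (Week 2) versus 3 months (Week 13), baseline versus 9 months (Week 37" and ends "and 3 months versus 9 months, using a paired t-test to evaluate the change in physical activity over time". It does not average adjacent weeks and has no rule for a missing step week.

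Protocol section 12 (P2E2T2 Program, item 2) describes where the data come from: "The selected sensors and applications will track numbers of steps traveled", and "The data wirelessly uploads to the participant's personal, or study supplied, Apple device". It adds: "Data elements shared to the electronic health record include: steps traveled, activities performed in minutes, calorie expenditure, and logged nutrition data". Section 26 confirms that physical activity data are stored in the clinical record. On duration, section 10 says: "Each individual will be enrolled in the study for 9 months".

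The SAP's mixed model is written for other outcomes: "The mixed effects models will evaluate the impact of the intervention over time in the outcomes of Diabetes Self-Efficacy, depressive symptoms" and perceived stress. A later SAP sentence extends the same approach to primary and secondary outcomes. Steps are not among the outcomes in protocol section 11 or in the section 14 measures table, and they have their own stated method, so that sentence does not clearly reach them.

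**The concern.** A paired t-test uses only participants observed at both of its time points. Someone who stops syncing before Week 37 stays in the first contrast and leaves the other two. Someone who misses only Week 13 stays in the Week 2 to Week 37 contrast alone. The three changes are then averages over three overlapping but different groups, and a reader who adds the change to 3 months to the change from 3 to 9 months may not recover the change to 9 months.

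A single week also carries all of that week's noise for that person, such as illness or travel, while neighbouring weeks that may already be uploaded are ignored. Protocol section 5 faults the earlier study for relying on self-reported activity and missing trends in behaviour, and the sensors were meant to close that gap. Steps are the only sensor-measured behaviour that the SAP analyses. For dropouts in its main comparison the SAP assumes missing at random and uses a mixed model. For steps, where unsynced weeks are an obvious source of gaps, it falls back on complete pairs.

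**Working it through.** The documents give no step mean, SD, effect size or sample size, so there is no stated step figure to reproduce.

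**1. Complete pairs.** Protocol section 7 plans at least 150 per arm, cites 16% attrition in the earlier study, and takes 100 per arm as a conservative case.
- A contrast involving Week 37, with 16% lost: 150 × 0.84 = 126 pairs. In the conservative case: 100 pairs.
- If each week were observed independently with probability p (assumption), pairs = 150 × p². For p = 0.95, 0.90 and 0.80 this gives about 135, 122 and 96.

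**2. Additivity.** For one person, (Week 13 − Week 2) + (Week 37 − Week 13) = Week 37 − Week 2. The same holds for means only if all three are taken over the same people. Separate complete-pair tests do not ensure that.

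**3. Precision.** Let d² be the variance of true individual change and w² the week-to-week variance within a person. Set r = w²/d², assumed to be 0.5 to 2. A 4-week mean has variance v·w².
- Independent weeks: v = 1/4 = 0.25.
- AR(1) correlation 0.5: v = [4 + 2(3×0.5 + 2×0.25 + 1×0.125)]/16 = 8.25/16 = 0.516.

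Variance of one person's change:
- two single weeks: d² + 2w²
- two 4-week means (weeks 10-13 and 34-37): d² + 2v·w²
- Week 2 against a 4-week mean: d² + (1 + v)w²

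Ratio to the single-week variance, with the reduction in brackets:

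| r | 3 v 9 months, independent | 3 v 9 months, AR(1) 0.5 | Baseline contrasts, independent | Baseline contrasts, AR(1) 0.5 |
|---|---|---|---|---|
| 0.5 | 1.25/2 = 0.625 (38%) | 1.516/2 = 0.758 (24%) | 1.625/2 = 0.813 (19%) | 1.758/2 = 0.879 (12%) |
| 1 | 1.5/3 = 0.50 (50%) | 2.031/3 = 0.677 (32%) | 2.25/3 = 0.75 (25%) | 2.516/3 = 0.839 (16%) |
| 2 | 2/5 = 0.40 (60%) | 3.063/5 = 0.613 (39%) | 3.5/5 = 0.70 (30%) | 4.031/5 = 0.806 (19%) |

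Two of the three contrasts start from the single baseline week, so they fall in the weaker columns.

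**4. Why a random intercept alone will not do.** Take two 4-week windows and independent weeks. A model with only a random intercept estimates the residual variance as (7w² + 2d²)/7 = w² + 2d²/7. It therefore reports a contrast variance of half that, 0.5w² + d²/7, per person. The true value is 0.5w² + d². At r = 0.5, 1 and 2 the ratios are 0.393/1.25 = 0.31, 0.643/1.5 = 0.43 and 1.143/2 = 0.57. The reported SE would be about 0.56, 0.65 and 0.76 of the correct one. The paired t-test does not have this fault.

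**The case against.** The strongest reply is that nothing here is wrong. Steps are not a listed endpoint, the SAP gives them one sentence, Weeks 13 and 37 roughly match the 3- and 9-month assessments, and a paired t-test at prespecified weeks is valid for the pairs it uses. That stands, and it makes this an optional improvement.

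A reader might infer that the plan throws away 33 of 36 weekly totals (Weeks 2 to 37). The documents do not support that. Thirty-six is a calendar span. No section says how many weeks reach the research dataset or that uploading continues after coaching ends, and section 14 lets participants filter what they share with the coach. What can be said is that any step data from other weeks go unused.

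A reader might also take 38-60% as the general gain. It needs independent weeks and applies only to the 3- versus 9-month contrast.

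Three limits on the remedy also stand. Weeks 10-13 lie within the 3-month coaching period, so pooling them changes what the 3-month value means. A participant with only one week has no observed change and adds little. If people stop syncing because they become less active, missing at random can fail and the mixed model will not remove that bias.

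Finally, more weeks do not supply a control. Section 9 says of the intervention group that the "arm will receive a health monitoring device at the beginning of the study", while usual care gets one only on completion. Section 14 describes technology set-up after randomisation into both arms, so those sections need reconciling. On section 9 the step analysis appears to be a before-after comparison in one arm.

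**Conclusion.** The point holds as a minor one about efficiency and coherence. As written, each step contrast drops participants missing either week, the three contrasts can describe different people and need not add up, and any other uploaded weeks are ignored. The SAP's mixed model does not clearly cover steps.

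The gain in precision cannot be fixed from the documents. Under the assumed variance ratio of 0.5 to 2, variance falls by about 24-60% for 3 versus 9 months and 12-30% for the baseline contrasts. The lower part of each range comes from AR(1) correlation 0.5 and the upper from independent weeks; stronger correlation would shrink the gain further.

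The documents do not support reading this as a flaw in the primary comparison or as proof that the step results would be biased.

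**What to change.** Replace the three paired t-tests with one repeated-measures mixed model on the available weekly step totals, with time as a factor. Let individual change vary, in one of two ways:
- one value per time point, with an unstructured covariance across the three; or
- all weekly totals, with random participant-by-period effects or slopes plus residual autocorrelation.

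Do not use a random intercept alone. Estimate the three changes, with 95% confidence intervals, as contrasts from that one model, so that they add up. If the three single weeks are kept and nobody is missing, the unstructured model gives the same changes as the paired t-tests.

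If adjacent weeks are pooled, for example 10-13 and 34-37, name the windows in advance and state that the 3-month value then includes coaching weeks. Keep the single-week paired t-tests as a sensitivity analysis. State the missing-at-random assumption, report how many participants contribute to each time point, and label the analysis as supporting and, if so, confined to the intervention arm.

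The cost is a few lines of SAP text and modest programming on data already uploaded, with no new collection.
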